Study: We will block randomize 88 chronic stroke patients to two treatment arms. Persons will be block randomized into anodal and sham tDCS conditions. Persons in the anodal tDCS condition will receive 20 minutes of stimulation and persons in the sham condition will receive 20 minutes of sham stimulation. All patients will receive gait training using a body weight supporting treadmill. In over ground assessments at baseline, weekly during gait training sessions, and one week, and one month post treatment, we will measure 1) gait velocity and spatiotemporal gait parameters using the GAITRite electronic walkway and 2) ankle, knee, and hip angles using motion analysis to gauge changes in the gait pattern. Cortical excitability will be measured at baseline, one week, and one month post treatment using transcranial magnetic stimulation (TMS). Functional MRI will be measured at baseline and after treatment between weeks 5-8. Additionally, we will measure change in physical function and social well-being using the Stroke Impact Scale and we will define patient characteristics that are associated with response to treatment.

Significance: If successful, this study will augment gait recovery and potentially increase the number of patients who benefit from gait training. Our methodological innovations will have application to a wide variety of neurological conditions.

Background and Rationale

Stroke is the leading cause of disability in the United States affecting 13 million people¹,². Up to two thirds of stroke survivors have significant limitations impairing their ability to walk³ including slow gait speed⁴ and changes in the quality of the gait pattern⁵. Additionally, individuals with a stroke and limited mobility are at high risk for subsequent complications including falls⁶, fractures⁷, and a further decline in mobility⁸. In contrast, recovering the ability to walk greatly improves quality of life and can return individuals to a previous level of productivity⁹⁻¹². Our proposal aims to use tDCS to

[figure not shown]
Version 10 Revised 11/21/2014

“jump start” the beneficial effect of gait training. This proposal is responsive to research priorities of the NINDS.

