2. Determine if active tDCS augments cortical excitability after gait training. Cortical excitability will be defined by a cortical recruitment curve, a primary outcome measure, derived from plots of motor evoked potentials (MEPs) recorded from the ipsilesional TA muscle. MEPs are elicited by single pulse transcranial magnetic stimulation (TMS) delivered at increasing intensity over motor cortex. Changes in the slope of the recruitment curve signal change in cortical excitability. Difference scores from baseline will be compared between active and sham groups to determine if tDCS augments cortical excitability after FESAGT. A repeat fMRI will be performed to assess change in cortical excitability after gait training.
3. Determine if active tDCS augments physical function and social wellbeing. The Stroke Impact Scale-16 (SIS-16), a primary outcome measure, will be used to assess ADL/IADL, mobility, and social and occupational engagement at baseline and post treatment assessments. Difference scores from baseline will be compared between active and sham groups to determine if tDCS augments physical function and social well-being.

Exploratory Aim

Identify patient characteristics that predict response to treatment. Patients will be classified empirically based on their response to treatments. Regression analyses will examine whether and how initial impairment, functional level, and cortical excitability predict a treatment response.

Study Interventions

tDCS and gait training will be conducted at UCA three times a week for 4 consecutive weeks

Version 10 Revised 11/21/2014

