Post-Intervention Procedures (Study Weeks 5(± 5 days) and 8 (± 10 days) :

During Study Weeks 1-5, and 8 Gait assessment (details provided in **Outcome Measures**) and the Stroke impact Scale 16 will be performed at UCA. During Study Weeks 5 and 8 TMS will be performed at UAMS and participants will complete a repeat fMRI scan. Details of TMS procedure used to establish recruitment curves are located in the Outcome Measures.

Reduction of Study Bias:

[name] will supervise delivery of interventions, and so, he will not be blinded to tDCS condition; however, Drs. [name] and [name] who collect and analyze data will be blinded to condition.

Study Locations:

tDCS, gait training, SIS-16, and the assessments of gait will take place in the Motion Analysis Laboratory at UCA; motor evoked potentials and recruitment curves developed from TMS are measured in the TMS and Human Electrophysiology core facilities at UAMS. Subject burden is reduced by requiring only four trips to UAMS over two - three months. (Subjects are informed that scheduling conflicts could result in an extra visit.) UAMS will be the IRB of record and Sponsor of the IDE.

Study Schedule

	Screening	Baseline	Study Weeks 1 -4 ^b	Study Week 5	Study Week 8
Consent	X				
Screening	X				
NIH Stroke Scale	X				
Modified Rankin Scale	X				
TASS	X				
Medical Record Review	X				
MRI	X			X	
Pregnancy Assessment	X				
Randomization	X				
Assessments					
Gait assessments		X	X	X	X
RC & SIS		X		X	X
Interventions					
tDCS			X		
Sham tDCS			X		
Gait training			X		

Definitions: TASS= Transcranial Magnetic Stimulation Adult Safety Screen, MRI=magnetic resonance imaging, RC & SIS-16=recruitment curve established using transcranial magnetic stimulation (TMS) and Stroke Impact Scale . ^bThree times a week for four weeks participants will receive active or sham tDCS and gait training interventions at UCA for a total of 12 treatment periods.

Study Population

Up to 100 stroke patients will be enrolled to obtain 88 who meet entry criteria and complete study procedures (i.e., 44 participants in each of the active or sham tDCS groups). Attrition, estimated at about 15%, will be handled by replacement.

Participants will be ≥21 years old to better represent the general stroke population. All participants will complete the NIH Stroke Scale, have evidence of gait impairment, and will be able to fully and safely participate in treatment.

Inclusion Criteria

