- Necessitates medical or surgical intervention to preclude a permanent disability or incapacity
- Results in a congenital anomaly or birth defect

Non-serious adverse events are all events that do not meet the criteria for a “serious” adverse event.

Severity:

Each adverse event will be assessed for its severity, or the intensity of an event experienced by the subject, using the following.

- Mild: Discomfort noticed, but no disruption to daily activity.
- Moderate: Discomfort sufficient to reduce or affect normal daily activity.
- Severe: Inability to work or perform normal daily activity.

Anticipated Adverse Events and Pre-existing conditions:

Pre-existing conditions will not be reported as an adverse event unless there has been a substantial increase in the severity or frequency of the problem which has not been attributed to natural history.

Data Handling and Recordkeeping

Each subject's name, birth date, address and phone number will be obtained for purposes of follow-up. We will ask for each subject's drug use history, medical history, and current drug use. Experimental data and questionnaire data will be collected. This information will be coded into the Microsoft Excel. Each subject's personal information will be de-identified in the database by using codes comprising the subject number and date and time the subject was tested. The PIs and study personnel at UAMS and UCA will have access to subject identities in order to arrange follow-up and to call them as part of the research project, such as follow-up contact. If subjects prefer e-mail correspondence research personnel will send e-mails for scheduling, follow-up, and research-related communication.

Data Analysis

Aims 1-3. Difference scores from baseline will be calculated for each outcome measure. A mixed model ANOVA with group (active tDCS groups versus sham tDCS) as the between subjects factor and time of assessment (pre, weeks 1-4, & one week and one month post) as the within subjects factor will be used to test all aims. A significant group effect, with active tDCS > sham tDCS, for any of the outcome measures would indicate that anodal tDCS augments gait training. A significant main effect of time would be evaluated using planned contrasts where we expect post treatment assessments to be improved relative to baseline. Interim analyses will be completed at critical stages during the protocol.

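### The deciding group effect averages change scores over the pre-treatment zero and four on-treatment weeks, so it does not estimate the post-treatment effect; no active-versus-sham contrast at a post visit is specified

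*Combined protocol and SAP*

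**What the plan says.** **Outcome and model (Data Analysis, Aims 1-3).** "Difference scores from baseline will be calculated for each outcome measure". The between-subjects factor is group, and the other factor is "time of assessment (pre, weeks 1-4, & one week and one month post) as the within subjects factor". One model serves everything: the time factor is entered "as the within subjects factor will be used to test all aims".

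**Deciding result.** "A significant group effect, with active tDCS > sham tDCS, for any of the outcome measures would indicate that anodal tDCS augments gait training". Follow-up comparisons are attached to time, not to group: "A significant main effect of time would be evaluated using planned contrasts where we expect post treatment assessments to be improved relative to baseline".

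**Visits by outcome.**
- Gait (Aim 1): "During Study Weeks 1-5, and 8 Gait assessment" is scheduled (Post-Intervention Procedures), in addition to baseline. This matches the seven levels.
- Recruitment curves (Aim 2): "Cortical excitability will be measured at baseline, one week, and one month post treatment using transcranial magnetic stimulation (TMS", according to the Protocol Summary. Post-Intervention Procedures and the Study Schedule agree, with nothing in weeks 1-4.
- SIS-16 (Aim 3): the Post-Intervention Procedures text puts it alongside gait in weeks 1-5 and 8. The Study Schedule marks it only at baseline, Week 5 and Week 8, and Specific Aim 3 refers to "social and occupational engagement at baseline and post treatment assessments".

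**Power.** The Power analysis paragraph uses another test, a 2 x 3 mixed MANOVA with interaction, with d = 0.39, r = 0.60 and alpha 0.05. It gives 37 per group for 85% power, and the trial is set at 88.

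**The concern.** The trial asks whether tDCS adds to the result of a four-week, 12-session programme. The natural answer is the active-sham difference once the programme is over. The stated rule instead decides on an average of seven values: one is zero by construction, four are taken while treatment is still being given, and only two come after it.

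Three things are at stake. The reported group difference would be on a scale that no reader would recognise as the treatment effect at follow-up. The sensitivity of the deciding test would depend on a time course that the plan does not describe. And with no active-sham contrast named at a post visit, that comparison would have to be chosen later, possibly with the data in hand. Aims 2 and 3 inherit a time factor whose levels they lack (Aim 2) or may lack (Aim 3).

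**Working it through.** **1. The plan's own figure.** Take d = 0.39 as a between-group difference, r = 0.60, compound symmetry, and the two-group, three-time interaction (noncentral F, df 2 and 2n - 3). For the pattern (0, d, d), the noncentrality is (n/2) x 2d²/[3(1 - r)] = 18.5 x 0.2535 = 4.69 at n = 37, and power is 46%. For (0, d/2, d) it is 36%. So 37 per group does not follow from the inputs as labelled. Entering 0.39 as a multivariate f comes close (84.5% at 37), but that departs from the stated label. In any case this is not the test that the Data Analysis section uses to decide.

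**2. Set-up for the stated test.** In a balanced design, the group effect is a two-sample t test on each participant's mean over visits. Inputs: r = 0.60 and d = 0.39 (Power analysis); 44 per arm (Study Population). Assumptions: SD 1 at every visit, compound symmetry, two-sided 0.05, and d read as the difference at Weeks 5 and 8.

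The mean of k post-baseline change scores has variance (1 - r)(1/k + 1).
- k = 6: 0.4 x 7/6 = 0.467, SD 0.683. Including the pre-treatment zero multiplies this by 6/7: SD 0.586.
- k = 2 (Weeks 5 and 8): 0.4 x 3/2 = 0.600, SD 0.775.

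**3. The pre-treatment level.** It multiplies both the mean and its SD by 6/7, so t, p and power do not move. A simulated data set gave t = 3.220 and p = 0.0018 both with and without it. What changes is the estimate: down by 1/7 with seven levels, and by 1/3 with three (baseline, Week 5, Week 8). The level also has zero variance, so an unstructured covariance matrix for all seven levels would be singular.

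**4. The on-treatment weeks.** The documents give no time course, so the profiles below are assumptions. Power is at d = 0.39. The mean of Weeks 5 and 8 has standardised effect 0.39/0.775 = 0.503 and power 65% in every row.

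| Effect at weeks 1, 2, 3, 4 (share of post effect) | Seven-level mean / post effect | Standardised effect | Power, stated test |
|---|---|---|---|
| 1, 1, 1, 1 | 6/7 = 86% | 0.571 | 75% |
| 0.25, 0.5, 0.75, 1 | 4.5/7 = 64% | 0.428 | 51% |
| 0.2, 0.4, 0.6, 0.8 | 4/7 = 57% | 0.381 | 42% |
| 0, 0, 0.25, 0.5 | 2.75/7 = 39% | 0.262 | 23% |
| 0, 0, 0, 0 | 2/7 = 29% | 0.190 | 14% |

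At an illustrative 0.5 SD, the second row becomes 72% against 85%, and the first 92% against 85%.

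**5. Break-even.** Let x be the mean week 1-4 effect as a share of the post effect. The two tests are equal when [(4x + 2)/6]/0.683 = 1/0.775, so x = (6 x 0.683/0.775 - 2)/4 = 0.82. Both SDs contain the factor √(1 - r), so r cancels. Below about 82%, averaging loses power; above it, averaging gains.

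**6. An effect that fades.** If the weekly effect were 1 and the post effect 0.5, the seven-level mean would be (4 + 1)/7 = 0.714, or 1.43 times the post effect.

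**7. Aim 2.** With its three real visits, the estimate is 2/3 of the post effect with the pre-treatment level and all of it without. Power is 65% either way.

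**The case against.** A reader might infer that the pre-treatment zeros weaken the test. They do not: step 3 shows that they rescale the estimate and its standard error equally.

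A reader might also infer that the stated test always understates the post-treatment effect and always costs power. The documents do not support that. The direction depends on an unstated profile. Gait is tested weekly during the training period, stimulation is given during training, and the background section says that excitability outlasts stimulation by about 30 to 90 minutes. The day and hour of the weekly test are not given. Testing inside that window is possible, and a large on-treatment effect would then raise the average. Nor are all four weeks clearly part-treated, because the week 4 test may follow the twelfth session. This objection stands, and the power loss must be stated as conditional.

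A third tempting reading is that the model cannot be fitted to Aim 2. A three-visit version can be fitted. The defect is that the text prescribes time levels which that outcome does not have.

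Finally, the text says group effect, not group main effect, and the power paragraph refers to a three-level interaction, so the authors may have meant something else. That is fair, but it means that the deciding test is unsettled between two sections. It does not supply the missing contrast.

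**Conclusion.** The point holds in a conditional form. From the text alone, with no assumption about the time course: the deciding rule, read literally, averages seven levels of a change score, one of them identically zero; it does not estimate the post-treatment effect; no active-sham contrast at a post visit is specified; the time factor does not fit Aim 2; the SIS-16 visits conflict; and the power paragraph addresses a different test.

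The size depends on assumptions: compound symmetry, equal SDs, d = 0.39 read as the post-treatment difference, and an assumed profile. Across the five profiles in the table, the seven-level mean is 29% to 86% of the post effect. Power runs from 14% to 75%, against 65% for the post-visit contrast. Gradual build-up favours the post-visit contrast; a full effect from the first week favours averaging. That the result turns on something the plan leaves open is itself the reason to name the contrast in advance.

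**What to change.** In Data Analysis, Aims 1-3:
- Remove the pre-treatment visit as a level of the change-score outcome. The planned comparison of post visits with baseline then becomes a test that mean change differs from zero, so nothing is lost.
- Prespecify, for each aim, the active-sham difference in change at the post-treatment visits as the deciding contrast: Weeks 5 and 8, or their mean.
- Keep weeks 1-4 as a secondary gait trajectory.
- List the visits by aim, with Aim 2 on Weeks 5 and 8.

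Reconcile the SIS-16 visits between the Post-Intervention Procedures text, the Study Schedule and Specific Aim 3. Weeks 5 and 8 are common to all three and can carry the Aim 3 contrast.

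Restate the power for that contrast. Under the working assumptions it is 65% at 44 per arm. By the normal formula, 85% needs 2 x (1.960 + 1.036)²/0.503², about 71 per arm, so the sponsor should say what the current sample size can detect.

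The cost is analysis wording and one schedule reconciliation, with no new data. The downside is a loss of precision if the full effect is already present in the first weeks: 65% rather than 75% power at d = 0.39, which is not negligible.

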Feasibility of obtaining valid TMS evoked recruitment curves for the TA muscle. In attempts to obtain recruitment curves for the TA muscle using a standard TMS coil, this study frequently exceeded stimulator output before the curve could become fully

established (i.e., plateau). In a series of normal subjects, this study overcame this limitation. First, by using a double cone coil which achieves deeper penetration of the magnetic field so TMS can be delivered at a lower intensity and, secondly, by having subjects make partial, isometric contractions of the TA muscle ipsilateral to stimulation (i.e., 20% of the maximum, volitional contraction: MVC). Contracting the ipsilateral limb enhances MEPs recorded from the contralateral limb (representative subject shown in Figure A, above). This method was then tested in normal subjects before, immediately following, and one hour after receiving active tDCS (10 [contact] anodal) or sham tDCS delivered over motor cortex. (representative subjects shown in B and C). MEP maximums increased after active tDCS for up to 1 hr and the recruitment curves became steeper indicating a lower threshold (i.e., an increase in cortical excitability). Similar changes were not seen for sham tDCS. During testing of our initial participants with stroke we found this technique to work for only one of three individuals. We will thus attempt to establish a motor threshold over the lesioned brain hemisphere for placement of tDCS electrodes and to establish participant characteristics for the exploratory regression analysis. Then we will obtain recruitment curves from stroke patients' intact hemisphere – having them contract the non-paretic, ipsilesional TA muscle at 20% MVC while a recruitment curve is obtained for the non-paretic, ipsilesional TA muscle. Additionally, we will assess the responsiveness of MEPs from the ipsilesional TA muscle after the administration of anodal tDCS to the lesioned cortex during our baseline assessments.

Feasibility of using tDCS with treadmill training in chronic stroke.

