In a pilot study investigating pairing locomotor training with transcranial direct current stimulation in patients with chronic stroke²³, our research collaborator at the University of Kentucky, [name], conducted a double-blind, randomized trial of active and sham tDCS (20 min at 2mA anodal stimulation over motor cortex) delivered just prior to locomotor training using a robotic gait orthosis treadmill. Eight participants (4 men, mean age=67.8; range=44-80) with chronic left hemisphere stroke (mean years post-stroke=4; range=1.1-11.6) were tested. Performance on a 10-meter walk test was the primary outcome measure, and assessments of functional ambulation category (FAC), timed up and go, balance, and the 16 item Stroke Impact Scale (SIS 16) were secondary measures. Improvement on the 10-meter walk test and the SIS 16 following active tDCS are shown in the figure - right. Active tDCS lead to greater improvement than sham tDCS on the FAC ($p=0.028$) and similar trends were evident for the SIS 16 ($p=0.062$) and the timed up and go test ($p=0.066$). This study shows that active tDCS augments gait training and function. The data were also used for power calculations.

Hypothesis and Specific Aims

Hypothesis: Increasing cortical excitability with active anodal tDCS prior to gait training will augment recover from a stroke.

Specific Aims:

1. Determine if active tDCS augments gait. Gait speed is a primary outcome measure. Spatiotemporal and kinematic gait assessment are secondary measures of gait. Over ground laboratory assessments of gait will measure 1) gait velocity and spatiotemporal gait measures using the GAITRite electronic walkway 2) ankle, knee, and hip angles using the SIMI motion analysis system. Changes in gait parameters will be expressed as difference scores from baseline. Difference scores will be compared between the active and sham groups to determine if tDCS augments gait parameters.

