Study Aim 2: Recruitment curves. A Magstim 200 super rapid2 stimulator with a 110 mm double cone coil will deliver stimulation. First, the TMS motor threshold (MT) will be established²⁷ and the best location for eliciting MEPs from the contralesional and ipsilesional TA muscle will be tracked on the subject's MRI scan in Brainsight. EMG will be recorded from the TA muscles of both limbs. The MT will be determined by placing the TMS coil over the cortical motor area and delivering single pulses of increasing intensity until the optimal area of stimulation is found. Threshold will be defined as the percentage of the maximum stimulator output necessary to elicit a motor evoked potential (MEP) of 50 μ volts recorded from the tibialis anterior muscle of the contralateral leg in 3 of 6 stimulus trials. Motor thresholds for both the lesioned and non-lesioned brain hemispheres will be recorded.

Second, recruitment curves will be obtained as follows: 1) delivering ten, single TMS pulses beginning at 70% of MT, 2) increasing TMS intensity by 10% and repeating the process up to 160% of the MT or until a plateau in the recruitment curve is reached, 3) offline data processing will be performed with the Matlab curve fitting toolbox and 4) the

threshold, slope, and MEPmax, and the goodness of fit (R^2) will be calculated. A change in the slope of the recruitment curve will indicate change in cortical excitability.

Study Aim 3: Functional and social assessments. The Stroke Impact Scale-16 (SIS-16, completed by study team) is a standardized instrument³⁶⁻³⁸ that assesses 3 functional domains in stroke patients including ADL / IADL, mobility, and social and occupational engagement.

Compensation

Participants will be remunerated \$200 for completing the entire study protocol. They will be remunerated \$75 dollars for partial completion.

Risks

A potential risk for study participation is the potential loss of confidentiality. Measures to protect the confidentiality of study participants will be implemented as described in the Data Handling and Recordkeeping section below.

Device Risks:

Potential risks associated with tDCS include the following:

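### The decision rule lets an active-better result on any outcome measure establish that tDCS augments gait training, which conflicts with the plan's own aims and with the outcome that sized the trial

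*Combined protocol and SAP*

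**What the plan says.** Under Specific Aims, each aim has its own primary outcome and its own question.

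- Aim 1 (gait): "Gait speed is a primary outcome measure". The next sentence ranks the other gait measures: "Spatiotemporal and kinematic gait assessment are secondary measures of gait".
- Aim 2 (excitability): "Cortical excitability will be defined by a cortical recruitment curve, a primary outcome measure". Outcome Measures, Study Aim 2, limits the inference: "A change in the slope of the recruitment curve will indicate change in cortical excitability".
- Aim 3 (function): "The Stroke Impact Scale-16 (SIS-16), a primary outcome measure", compared between groups "to determine if tDCS augments physical function and social well-being".

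The Power analysis bases the sample size on a meaningful change in gait speed, at an alpha of 0.05. That is the only alpha in the document, and its sidedness is not stated.

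The Data Analysis section, Aims 1-3, applies one mixed-model ANOVA to the difference scores of every outcome measure and then gives the rule: "A significant group effect, with active tDCS > sham tDCS, for any of the outcome measures would indicate that anodal tDCS augments gait training". The same paragraph says that interim analyses will be done, without giving their number, timing or alpha.

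**The concern.** The rule merges three separate questions into one claim about gait training and lets any measure answer it. The primary and secondary labels in the aims play no part in it. No section supplies a testing order, a division of alpha, a requirement that all primaries succeed, or a correction. The planned contrasts in the same paragraph concern only the effect of time.

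Two things are at stake. The first is meaning: a secondary joint angle, or a recruitment curve, would count as evidence that gait training was augmented even if gait speed did not differ. The curve is taken from the undamaged side (Preliminary studies: "we will obtain recruitment curves from stroke patients' intact hemisphere"), and by the plan's own account its slope speaks only to excitability. The second is error: each further measure gives another chance of a false claim, while the sample size was justified on gait speed alone.

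**Working it through.** The plan states no error rate for this rule, so there is no figure of its own to reproduce.

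**Inputs from the documents.** Alpha 0.05 (Power analysis); three measures labelled primary (Specific Aims); only active-better results count (Data Analysis).

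**Assumptions.** Each test is two-sided, with one test per outcome and no interim looks. Correlations between outcomes are not given, so a range is shown. The number of secondary measures is not given either, so only one is added.

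**One test.** The chance of a false active-better result is 0.05 / 2 = 0.025, or 2.5%.

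**k independent tests.** Chance of at least one false claim = 1 − 0.975^k.
- k = 3: 1 − 0.975³ = 7.3%
- k = 4: 1 − 0.975⁴ = 9.6%

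**k tests with common correlation ρ.** Chance = 1 − ∫ φ(u) · Φ[(1.96 − √ρ·u) / √(1 − ρ)]^k du, by numerical integration.

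| Correlation | Three primaries | Three primaries plus one secondary |
|---|---|---|
| 0 | 7.3% | 9.6% |
| 0.3 | 6.8% | 8.7% |
| 0.5 | 6.3% | 7.8% |
| 0.7 | 5.5% | 6.5% |
| 0.9 | 4.2% | 4.7% |

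Each further secondary measure adds at most 2.5 percentage points.

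**Sidedness.** If each test were one-sided at 0.05, a single test would give 5% and three independent tests 1 − 0.95³ = 14.3%.

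**Interim looks.** As an illustration, assume equally spaced looks, each tested at two-sided 0.05 without adjustment, and count only active-better results. The statistics at looks i < j have correlation √(i/j). A single gait-speed test then has a false-claim rate of 4.2% with two looks in total and 5.4% with three. The 2.5% baseline therefore holds only without interim testing, or with interim testing under an alpha rule.

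**The case against.** The strongest reply is that the sentence is loose shorthand. It stands under a heading for Aims 1-3, the model is said to test all aims, and nothing withdraws the aim-specific conclusions. Aims with separate conclusions need not share one alpha. This much stands: three primaries for three separate claims would not in itself be a fault. But the sentence is the only efficacy rule in the Data Analysis section, and it draws one gait-training claim from any measure. If it is shorthand, it should be replaced with what is meant.

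It is also fair to say that the inflation is modest when the three primaries are strongly correlated, and that Aim 1 speaks of gait parameters generally. Making gait speed the sole basis therefore narrows that aim.

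Three stronger readings are tempting, and the documents support none of them.

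- A reader might infer that an excitability-only win is likely, because the Preliminary studies report larger MEPs after active tDCS. That rise lasted up to one hour in normal subjects. Post-treatment curves are scheduled at Weeks 5 and 8, and Study Interventions places the cathode over the hemisphere opposite the lesion, which is the one the curves come from. The Background says that cathodal stimulation lowers excitability.
- A reader might quote 14.3% as the false-claim rate. With two-sided tests that figure counts results in either direction, whereas the rule counts only active-better results.
- A reader might take this point to show that the sample size is wrong. How the effect size of 0.39 is to be read, and what power follows, is a separate matter.

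**Conclusion.** The rule is wrong as written, which is more than a missing detail. It contradicts the aim-specific conclusions and the secondary labels in the Specific Aims, and it does not match the gait-speed basis of the sample size. That conflict holds whatever the error rate.

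For the three primaries alone, the false gait-training claim rate is 4.2% to 7.3% over correlations of 0.9 to 0. With one secondary added it is 4.7% to 9.6%. A single gait-speed test gives 2.5%. These figures assume two-sided 0.05 tests, one test per outcome, no true effect and no interim looks. Unadjusted interim testing would raise all of them, including the 2.5%.

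**What to change.** In Data Analysis, Aims 1-3:

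1. Make gait speed, in place of any outcome measure, the basis for the claim that tDCS augments gait training.
2. Limit recruitment-curve conclusions to Aim 2 (cortical excitability) and SIS-16 conclusions to Aim 3 (physical function and social well-being).
3. Report spatiotemporal and kinematic measures as supportive, with confidence intervals.
4. Name the single gait-speed test that decides. Data Analysis relies on the group effect, whereas the Power analysis describes a design with an interaction.
5. State the number and timing of the interim analyses and whether they test efficacy. If they do, give the alpha rule.

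If the sponsor wants one trial-wide error rate across the three primaries, a prespecified fixed sequence starting with gait speed at 0.05 is one option.

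The cost is a protocol amendment submitted to the IRB. The wording change needs no new data or participants. The downside is that a positive SIS-16, TMS or secondary gait result would no longer support the gait-training claim by itself, and Aim 1's conclusion narrows from gait parameters to gait speed. The change should be made before anyone sees outcomes by group, because a rule chosen afterwards would not be credible.
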